6.3. Dose Limiting Toxicities (DLTs)

DLTs will be defined as a TEAE or abnormal laboratory value related to study treatment (i.e., assessed as unrelated to disease, intercurrent illness, or concomitant medications), including those TEAEs and abnormal laboratory values that result in a failure to meet the criteria for retreatment. DLTs will be considered related to the study treatment unless there is clear evidence of an alternative explanation and this attribution is agreed to by the CRC.

For the purposes of dose escalation and determination of the MTD, only DLTs that occur during the first cycle will be necessarily considered for decisions regarding dose escalation. Clinically significant toxicities or treatment-emergent adverse events that meet the definition of dose limiting but occurring after Cycle 1 (dose modifying events) may be considered when determining the RP2D.

A listing of DLTs will be provided.

6.4. Clinical Laboratory Results

Laboratory test results (including hematology, coagulation, serum chemistry, and urinalysis) and abnormal laboratory values will be presented in data listings. CTCAE v4.03 lab grades will also be presented for those tests which have associated grading criteria. CTCAE grades will be derived based on laboratory results, and will not factor in clinical evaluations.

Shift tables summarizing the changes from baseline in severity of lab grades will be provided for lab parameters that are graded according to the CTCAE v4.03. Summaries of actual values and changes from baseline will be presented by treatment group for each assessment time point, beginning with the first post-baseline assessment. Grade 3 or above lab values will also be summarized based on the worst grade observed on study.

For the liver function tests, a summary of clinically significant values in liver function tests will be reported by the following categories using the maximum value while on treatment. The denominator for the summaries will be the number of patients who had at least one non-missing value during treatment. Note the categories for each test are not mutually exclusive:

- Aspartate Aminotransferase (AST)
 - >3xULN
 - >5xULN
 - >10xULN
 - >20xULN
- Alanine Aminotransferase (ALT)
 - >3xULN
 - >5xULN
 - >10xULN
 - >20xULN
- AST or ALT
 - >3xULN
 - >5xULN
 - >10xULN
 - >20xULN

- Total Bilirubin (TBL)
 - >1.5xULN
 - >2xULN
- Alkaline Phosphatase (ALP)
 - >1.5xULN
- (AST or ALT) and TBL
 - AST or ALT >3xULN and TBL >1.5xULN
 - AST or ALT >3xULN and TBL >2xULN
- (AST or ALT) and ALP and TBL
 - AST or ALT >3xULN and ALP <2xULN and TBL \geq 2xULN

Results from pregnancy tests will be provided in data listings.

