Schedule B, the starting dose of IMGN853 was 1.1 mg/kg, which was 1/3 the 3.3 mg/kg dose level, which was deemed clinically safe in nine patients on a Q3W schedule. All doses were calculated according to adjusted ideal body weight (AIBW). Patients were enrolled in cohorts of 3 to 6 patients and the MTD was determined to be 2.0 mg/kg (AIBW). The CRC to review safety, PK and efficacy data from the dose escalation cohorts, as well as available data from patients treated on Schedule A. The modified weekly schedule did not provide any apparent

ImmunoGen, Inc. Confidential Page 55 of 138

safety or efficacy advantage. These results were presented at the annual ASCO meeting (Borghei 2015).

Based on safety and overall response data collected through May 2015, the CRC determined that all new patients enrolled in the trial will receive IMGN853 at the MTD of 6 mg/kg once every three weeks. Safety data available to date indicate that the MTD is equal to the RP2D. Moving forward, Schedule B will not be evaluated any further in this study; however, patients enrolled to Schedule B prior to the CRC decision, will continue on this schedule.

The period of observation extends from the time the patient receives the first dose of IMGN853 until the final follow-up study visit. Patients will continue to receive IMGN853 until unacceptable toxicity or withdrawal of consent, whichever comes first, or until the Sponsor terminates the study. Patients who meet the RECIST criteria for PD while on study may remain on study, provided there is evidence of clinical benefit and no unacceptable toxicity, as agreed upon by the Investigator and the medical monitor. Patients who discontinue study drug for reasons other than PD will be followed until PD, start of new anti-cancer therapy, or death, whichever occurs first.

The primary aims of the Dose Expansion phase are to further evaluate safety and tolerability and to assess IMGN853 Pd and preliminary efficacy.

CTCAE version 4.03 will be used to grade adverse events.

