APPENDIX A. SCHEDULE OF CLINICAL ASSESSMENTS –SCHEDULE A (Q3W)

			Cycle 1			Cycle	e 2		Cycle	3	Cycles ≥4	End of	28-Day
Activity	Screening	Day 1	Day 2	Day 8&15	Day 1	Day 8&15	Day 18±3	Day 1	Day 2	Day 8&15	Day 1	Treatment	Follow-up (+14 Days)
Informed consent	•a												
Demography	•a												
Medical History	● ^a												
Confirm Disease Diagnosis/Current Stage and Prognostic Index Evaluation	●a												
Record Baseline Signs and Symptoms	•	•											
Review and document IC/EC (Sections 3.1 and 3.1.2)	•c												
Confirm patient continues to satisfy I/E Criteria (Sections 3.1 and 3.1.2)		•											
Confirm patient meets retreatment criteria (Section 5.9.3)					•			•			•		
Height	● ^a												
Physical Examination ^b	• c	•		•	•	•		•			•	•	•
Weight	● ^c	•			•			•			•	•	•
Vital signs ^d	● ^c	•	•		•			•	•		•	•	•
Pulse oximetry		•	•	•	•	•		•	•	•	•	•	•
Pulmonary Function Test ^e	•												
ECOG PS	• c	•			•			•			•	•	•

			Cycle 1			Cycle	e 2		Cycle	3	Cycles ≥4	End of	28-Day
Activity	Screening	Day 1	Day 2	Day 8&15	Day 1	Day 8&15	Day 18±3	Day 1	Day 2	Day 8&15	Day 1	Treatment	Follow-up (+14 Days)
Hematology and Chemistry	● c	$ullet^{\mathrm{f}}$		•	•	•		•		•	•	•	•
Coagulation (PT/INR/aPTT)	• c	• f			•			•			•		•
Urinalysis	•c	● ^f			•			•			•		•
Pregnancy Test (urine or Serum) ^g	• c	•					Even- numbered cycles (2, 4, 6, etc.) ^g						•g
Ophthalmic examinationsh	•						Every other cycle (from point at which toxicity first reported)h					•	•
Schirmer Test ^h	•						-emergent eye mic examinati indicated						
Ocular Symptom Assessment ^h		•			•			•			•	•	•
Radiologic tumor assessments	● ^a						Every 6 weeks ± 1 week) ⁱ					•j	•j
CA125 (Appendix F)	• c						Every 6 weeks(± 1 week) ⁱ					•j	•j
12-Lead ECG (Section 8.7) ^k	●c	•	•					•	•			•	•1

			Cycle 1			Cycle	e 2		Cycle	3	Cycles ≥4	End of	28-Day
Activity	Screening	Day 1	Day 2	Day 8&15	Day 1	Day 8&15	Day 18±3	Day 1	Day 2	Day 8&15	Day 1	Treatment	Follow-up (+14 Days)
Neuropathy assessment, including FACT/GOG- Neurotoxicity Questionnaire	● c	•			•			•			•		•
IMGN853 Infusion		•			•			•			•		
Corticosteroid Eye Drops		Patients in Expansion Cohort 5 (only) will self-administer corticosteroid eye drops as described in Section 5.8.2											
Lubricating Eye Drops		Α	ll patier	nts will s	elf-adm	inister lu	bricating eye	drops a	as descri	bed in Sec	tion 5.8.3		
AE and SAE assessments	● ⁿ	•		•	•	•		•	•	•	•	•	•
Record concomitant medications	● c	•		•	•	•		•	•	•	•	•	•

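### SAP 6.4 builds the combined liver categories from each test's on-treatment maximum, so the ALP-restricted row can lose a patient who met all its conditions at one draw, and all three combined rows can count elevations that never coincided

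*SAP*

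**What the plan says.** SAP Section 6.4 (Clinical Laboratory Results) introduces the liver summary with one sentence: "a summary of clinically significant values in liver function tests will be reported by the following categories using the maximum value while on treatment". The next sentence sets the denominator: "The denominator for the summaries will be the number of patients who had at least one non-missing value during treatment". Single-test rows for AST, ALT, AST or ALT, total bilirubin (TBL) and ALP come first, followed by three combined rows:

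- "AST or ALT >3xULN and TBL >1.5xULN"
- "AST or ALT >3xULN and TBL >2xULN"
- "AST or ALT >3xULN and ALP <2xULN and TBL", completed by a bilirubin bound of at least 2xULN

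ALP in the third row is the only component in the table with an upper limit. The section sets no same-draw or time-window condition for the combined rows, and I found none elsewhere in the SAP or protocol. The same section also plans full listings: "Laboratory test results (including hematology, coagulation, serum chemistry, and urinalysis) and abnormal laboratory values will be presented in data listings".

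**The concern.** A maximum suits a row that asks whether one test ever exceeded a threshold. A combined row is normally read as describing abnormalities that occurred together. Built from separate maxima, it describes abnormalities that each occurred at some time on treatment.

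The gap can be long in this trial. Protocol Section 4.1.1 states: "Patients will continue to receive IMGN853 until unacceptable toxicity or withdrawal of consent, whichever comes first". It also allows treatment beyond RECIST progression where there is clinical benefit. A bilirubin or ALP rise late in the disease course can therefore fall on treatment, well after a transaminase peak. Protocol Section 3.1.1 admits patients with liver metastases whose AST and ALT are below 5xULN, so some may start above the 3xULN threshold and need only a later bilirubin rise to be counted.

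At stake is the accuracy of the only planned summary of joint liver abnormalities in a first-in-human study. The ALP row matters most, because it is meant to separate transaminase and bilirubin rises without marked ALP elevation from the rest.

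**Working it through.** The plan states no figure on this point, so there is nothing to reproduce. The check applies the written rule and a same-draw rule to the same data.

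**Inputs from the documents**

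- Rule and row definitions: SAP Section 6.4.
- Panel: Protocol Table 13 (Section 8.10.1) puts ALP, ALT, AST and total bilirubin in one serum chemistry panel.
- Timing: the Protocol Appendix A line "Hematology and Chemistry" places draws on Days 1, 8 and 15 of Cycles 1 to 3, Day 1 of each cycle from Cycle 4, end of treatment and the 28-day follow-up. Same-draw values therefore exist.

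**Step 1: logic.** At draw t, let A(t) be the larger of AST and ALT, T(t) bilirubin and P(t) ALP, all in xULN.

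- *Rows without ALP (c = 1.5 or 2).* The written rule is max A > 3 and max T > c. A same-draw rule asks for some t with A(t) > 3 and T(t) > c. Any same-draw case satisfies the written rule, but the converse fails. Maxima can only over-include here.
- *ALP row.* The written rule is max A > 3, max T ≥ 2 and max P < 2. Since max P < 2 means P(t) < 2 at every draw, one ALP value of 2 or more at any visit excludes the patient. Neither rule implies the other, so errors run both ways.

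**Step 2: illustrative profiles.** The values are assumed, to show the mechanism only. On Schedule A, Day 1 of cycle k is study day 1 + 21(k − 1). Days 22, 64, 106 and 148 are then Day 1 of Cycles 2, 4, 6 and 8. Each result cell reads written rule / same-draw rule.

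| Profile | Key draws (xULN) | Maxima A, T, P | A>3, T>1.5 | A>3, T>2 | ALP row |
|---|---|---|---|---|---|
| A | Day 22: ALT 6, TBL 2.5, ALP 1.2; Day 106: ALP 2.4 | 6, 2.5, 2.4 | yes / yes | yes / yes | **no / yes** |
| B | Day 22: ALT 4, TBL 0.8; Day 148: ALT 1.1, TBL 2.3 | 4, 2.3, 1.3 | **yes / no** | **yes / no** | **yes / no** |
| C | Day 22: ALT 6, TBL 2.5, ALP 1.2; ALP never higher | 6, 2.5, 1.2 | yes / yes | yes / yes | yes / yes |
| D | Day 8: ALP 2.1; Day 64: ALT 5, TBL 2.2, ALP 1.5 | 5, 2.2, 2.1 | yes / yes | yes / yes | **no / yes** |

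**Step 3: results.**

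- Profile A meets all three conditions on Day 22 and is removed from the ALP row by an ALP value 106 − 22 = 84 days later.
- Profile D shows that an earlier ALP rise does the same.
- Profile B counts in all three combined rows although its ALT and bilirubin elevations are 148 − 22 = 126 days apart and never coincide.
- Profile C, the control, is classified identically under both rules.

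**Step 4: boundary.** The ALP row uses bilirubin at or above 2xULN, while the second combined row uses strictly above. With ALT 4, TBL exactly 2.0 and ALP 1.0, a patient meets the 1.5xULN row and the ALP row but not the 2xULN row. If such a patient's bilirubin never goes higher and ALP reaches 2xULN at another visit, only the 1.5xULN row keeps the case.

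**The case against.** The other side has substantial points.

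- **The case stays in the table.** A reader might infer that a true concurrent case vanishes from the liver summary. The documents do not support that. Step 1 shows that the two rows without ALP cannot lose a concurrent case that meets their thresholds; the loss is confined to the ALP row. This stands.
- **The table drives no decision.** It is descriptive, and no dosing, stopping or MTD rule refers to it. Monitoring runs through laboratory review before each dose (Protocol 8.10), adverse event recording of clinically significant values (9.1.1.1) and the DLT criteria, with CT work-up of unresolved dose-limiting hepatic toxicity (4.1.4). This stands.
- **Cases can be checked.** The listings are ordered by patient and time of assessment (SAP 3.8), so a reader can see whether elevations coincided. No data are lost. This stands, but hand checking does not correct the printed count.
- **A strict same-visit rule has its own error.** From Cycle 4 on Schedule A, chemistry is scheduled only about every three weeks, so related rises may fall on adjacent draws. This stands and shapes the fix.
- **The table shells are a separate document** (SAP 1.1) and may define the rows further. That is possible, but the SAP text already states a rule, and a programmer following it would combine maxima. A different derivation in the shells would conflict with the SAP and need reconciling.

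**Conclusion.** The point holds. As written, the ALP row can omit patients who met all its conditions at one draw, and all three combined rows can include patients whose transaminase and bilirubin elevations never coincided. This follows from the stated rule and does not depend on any assumed rate.

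The size cannot be estimated, because the documents give no frequencies for these elevations. A reader might try to size the loss by assuming that some share of patients reach ALP 2xULN at another visit. If that is independent of being a true case, the share of same-draw cases lost from the ALP row simply equals the assumed share. Such a figure would restate its input and would apply to one row, not to the whole table.

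The consequence is limited to counts in a descriptive safety summary. It is worth correcting because the rows will be read as simultaneous events and the correction is cheap. The conclusion assumes that the rule in Section 6.4 is applied literally. If the sponsor meant maxima for the single-test rows only, the SAP should say so.

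**What to change.** Amend SAP Section 6.4 as follows; Section 1.1 allows changes until database lock.

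1. Keep the on-treatment maximum for the single-test rows.
2. For the ALP row, evaluate bilirubin and ALP at the same draw as the AST or ALT elevation, or within a pre-stated window of it. If a window is used, state which ALP value in it counts.
3. For the two rows without ALP, keep the maximum-based count, labelled as a sensitive screen that does not require coincidence. Beside it, add the number of patients whose elevations fall within the same window.

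The cost is slight extra programming and no new data. The risk lies in the choice of window. With scheduled draws about three weeks apart from Cycle 4 on Schedule A, a shorter window would in effect be a same-draw rule there, apart from unscheduled tests, and could miss pairs on adjacent draws. The width should be fixed with that spacing in mind and before the counts are seen.

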6.5. Immunogenicity

The potential immunogenicity against IMGN853 or DM4 will be assessed at various time points in Cycles 1 through 6, as outlined in [Protocol Section 6.3](#) and [Protocol Appendix C](#). Exploratory analyses will be completed to evaluate the potential impact of immunogenicity on PK, safety, and efficacy.

6.6. Vital Signs and Pulse Oximetry

Vital signs (including temperature, pulse rate, systolic blood pressure, diastolic blood pressure, respiratory rate and weight, pulse oximetry) will be presented in data listings. Summaries of actual values and changes from C1D1 pre-dose baseline at each time point will be presented.

6.7. Electrocardiograms

Electrocardiograms (ECG) results (Rhythm, Heart Rate, PR Interval, RR Interval, QRS Interval, QT Interval, QTcF Interval, and classification of Within Normal Limits, Abnormal, Not Clinically Significant, and Abnormal, Clinically Significant will be presented in data listings. If a different correction for QT is captured in the eCRF, that QTc will also be reported in the listing for that patient along with QTcF.

The number and percent of patients in the following non-mutually exclusive categories will be summarized by visit:

- QTc >450 ms
- QTc >480 ms
- QTc >500 ms
- QTc change from baseline >30 ms
- QTc change from baseline >60 ms

Note that dosing ECGs are collected in triplicate; analyses for replicated results will be based on the average of the replicate results. The QTcB and QTcF collected on eCRF will not be used in this summary table. Instead, for this summary table, QTcB and QTcF will be derived from QT and RR:

$$QTcF = \frac{QT}{\sqrt[3]{RR}}$$
$$QTcB = \frac{QT}{\sqrt{RR}}$$

Where QT and RR are both measured in seconds.

For the overall ECG result (Within Normal Limits, Abnormal, Not Clinically Significant, and Abnormal, Clinically Significant) summaries will be provided for baseline and each post-baseline assessment time point. Note that dosing ECGs are collected in triplicate and analyses for the overall ECG result will be based on the worst-case result (i.e. if any one of the triplicate results is Abnormal, Clinically Significant then the value for the time point will be Abnormal, Clinically Significant). The hierarchy for the worst-case assessment is: Abnormal, Clinically Significant will be considered the worst value, with Abnormal, Not Clinically Significant being considered worse than Within Normal Limits.

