8.7. Electrocardiogram (ECG)

A standard, single 12-lead electrocardiogram (ECG) will be performed within 14 days prior to first dose to determine study eligibility.

On study ECGs will be performed in triplicate at the following timepoints in Cycles 1 and 3:

- Baseline ECG: Within one hour prior to the first dose
- Post Dose ECGs:
 - \circ End-of-infusion to coincide with C_{max} and PK blood draw (within one hour from this blood draw)
 - \circ 24 ± 2 hours post infusion to coincide with PK blood draw

Triplicate ECGs will be performed at 2-5 minute intervals. A single ECG will also be performed at the end of treatment visit and as clinically indicated (Appendix A and Appendix B).

Vital signs (blood pressure, pulse, and respiratory rate) will be measured within 10 minutes of completion of each set of triplicate ECG readings.

ImmunoGen, Inc. Confidential Page 86 of 138

 $^{^{\}rm b}$ \pm 10 minutes

^c Within 10 minutes following completion of infusion

^d Cycles 1 and 2 only. If the patient's infusion was well-tolerated, the 4-hour post infusion assessment will not be required in Cycles ≥3.

^e Measured predose and within 10 minutes of completion of each set of triplicate ECG readings (predose, end of infusion to coincide with C_{max} PK draw (+10 minute window) and 24 hrs post infusion (±2 hours) – See also Section 8.7.

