11. STATISTICAL METHODS

All descriptive statistical analyses will be performed using the most recently released and available SAS statistical software, unless otherwise noted. For categorical variables, the number and percent of each category within a parameter will be presented. For continuous variables, the sample size (n), mean, median, and standard deviation, as well as the minimum and maximum values, will be presented. Missing data will not be imputed unless otherwise stated. There will be a detailed description of patient disposition, patient demographics, and baseline characteristics.

No formal interim analysis is planned for this study. However, a review of safety data and available preliminary PK data will be conducted by the CRC after the MTD or a RP2D for IMGN853 has been determined. Results from this data review could enable selection of dose and dosing schedule for additional studies with IMGN853, before full completion of this study.

A statistical analysis plan (SAP) will fully describe the planned analyses for this trial. All analyses will be performed for any patient that received study drug. All analyses for efficacy will use Cycle 1, Day 1 as the start time.

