11.3. Safety Analyses

Adverse events, concomitant medication, and results from physical examination will be listed.

Adverse events will also be coded with the Medical Dictionary for Regulatory Activities (MedDRA; version 17.0 or greater) and summarized per system organ class (SOC) and preferred term.

ImmunoGen, Inc. Confidential Page 107 of 138

Concomitant medications will be coded using the World Health Organization Drug Dictionary (WHO-DD; June 1, 2012 or later version). A dictionary listing of all unique concomitant medications used in the study will be provided.

All hematology, blood chemistry, vital signs, and ECG results will be listed per patient for each assessment and descriptive statistics will be tabulated for select criteria. Changes from baseline in hematology, blood chemistry, vital signs, and ECG results will be summarized by treatment. Shifts in hematology and blood chemistry from Baseline values will be summarized. Plasma also will be evaluated for the presence of humoral responses against the M9346A antibody component (HAHA) or against the DM4 component (HADA).

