3.8. Data Display Characteristics

Data displays produced for this study will include data listings, summary tables, and figures. Unless stated otherwise, data listings will be produced for all recorded data. Summary tables will be produced as specified in following sections. Additional data listings will be produced for outcome measures that involve extensive procedures to derive the analyzed outcomes. Figures will be produced when specified in sections to follow. Final delivery of tables, listings, and figures will have numbering in compliance with the ICH E3 guideline. Prior to compilation of the clinical study report, Novella standard TREF, FREF, and LREF reference numbers will be used.

Data listings will simply list the data recorded in the eCRF or derived for each patient. They will be ordered by phase (escalation or expansion), cohort, patient number, and time of assessment. When expedient, additional levels of ordering hierarchy may reflect subsets of assessments within patient. Data listings will not display patient initials.

Summary tables will display summary statistics calculated for each of the dose cohorts or treatment groups, unless described otherwise in following sections. See shell tables for specific formats.

The summary statistics displayed will be a function of the type of data associated with the summarized assessment. For categorical variables, the number and percent of each category within a parameter will be calculated. For continuous variables, the sample size (n), mean, median, and standard deviation, as well as the minimum and maximum values, will be presented. Some continuous variables may also be grouped into categorical levels and evaluated in frequency tables.

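### SAP 6.7 specifies no continuous change-from-baseline summary for any ECG interval, although Protocol 11.3 says ECG changes from baseline will be summarized

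*SAP*

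**What the plan says.** **Collection.** Protocol 8.7: "On study ECGs will be performed in triplicate at the following timepoints in Cycles 1 and 3". The time points are pre-dose, end of infusion (timed to the Cmax blood draw, with a one-hour allowance) and 24 hours. A single ECG is taken at end of treatment.

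**Protocol analysis.** Protocol 11.3 says ECG results, along with laboratory data and vital signs, "will be listed per patient for each assessment and descriptive statistics will be tabulated for select criteria". It then says: "Changes from baseline in hematology, blood chemistry, vital signs, and ECG results will be summarized by treatment". The default format in Protocol Section 11 is: "For continuous variables, the sample size (n), mean, median, and standard deviation, as well as the minimum and maximum values, will be presented".

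**SAP analysis.** SAP 6.7 averages the triplicates and then plans one QTc table: "The number and percent of patients in the following non-mutually exclusive categories will be summarized by visit". The categories are QTc above 450, 480 and 500 ms and change from baseline above 30 and 60 ms. A second table gives the overall ECG class (normal; abnormal, with or without clinical significance) by time point. All other ECG results are listed.

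**Comparable sections.** For vital signs, SAP 6.6 says: "Summaries of actual values and changes from C1D1 pre-dose baseline at each time point will be presented". SAP 6.4 plans the same for laboratory values. SAP 3.8 says: "Summary tables will be produced as specified in following sections".

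**The concern.** Protocol 11.3 names ECG results in the same sentence as laboratory data and vital signs. The SAP carries that sentence through as continuous change summaries for the other two but not for ECGs, and neither document says why.

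Averaging triplicates buys precision, and cutting the average at 30 ms then discards most of it. A modest average shift moves few patients across the line, so a table with few counts can look reassuring while the recorded values have moved. For heart rate, PR and QRS no change table of any kind is specified. The phrase 'by visit' also leaves open whether the pre-dose and end-of-infusion readings on Day 1 are tabulated separately, which matters because the latter is timed to peak concentration. This is the first-in-human study that sets the recommended Phase 2 dose.

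**Working it through.** **1. Is the summary specified elsewhere?** Side by side:

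| Data | Promised in Protocol 11.3 | Specified in the SAP |
|---|---|---|
| Laboratory | change from baseline | actual values and changes (6.4) |
| Vital signs | change from baseline | actual values and changes (6.6) |
| QTc | change from baseline | counts above +30 and +60 ms only (6.7) |
| Heart rate, PR, QRS on ECG | change from baseline | none; listings only (6.7) |

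SAP 3.8 refers to later sections for its tables, and no later section names a continuous ECG table.

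**2. How much information do the cut-points lose?** The documents state no QTc effect, SD or power, so there is no ECG figure to reproduce. As a check on the binomial routine, it matches all 18 cells of Protocol Table 16 (SAP Table 4) to within 0.001; for example 1 - 0.9^40 = 0.985.

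Inputs from SAP 2.3.3.2: cohorts of 40 and 20 patients; all expansion patients 40 + 20 + 20 + 20 + 40 = 140.

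Assumptions, not in the documents: the change in triplicate-mean QTc is normal with SD s = 12, 15 or 20 ms; the true mean shift is d = 5, 8 or 10 ms; one time point is examined. No test is planned in the study, so power serves here only as a measure of information.

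Formulas:
- Chance that one patient exceeds +30 ms: p(d) = 1 - Φ((30 - d)/s).
- Count: c is the smallest number with P(Bin(n, p(0)) ≥ c) ≤ 0.05; power = P(Bin(n, p(d)) ≥ c).
- Mean: power of a one-sided 5% one-sample t test, with non-centrality d√n/s.

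Worked case, n = 40, s = 15, d = 8:
- p(0) = 1 - Φ(2.00) = 0.0228, giving c = 4 with a true level of 1.3%.
- p(8) = 1 - Φ(22/15) = 0.0712, so count power is 32%.
- Non-centrality = 8 × 6.325/15 = 3.37, so mean power is 95%.
- With the t test held to the same 1.3% level, its power is 85%. Of the 63-point gap, about 10 points come from the mismatch in level and 53 remain.

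All cells at n = 40 (count vs mean):

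| SD | 5 ms | 8 ms | 10 ms |
|---|---|---|---|
| 12 | 17% vs 83% | 39% vs 99% | 58% vs 100% |
| 15 | 12% vs 67% | 32% vs 95% | 50% vs 99% |
| 20 | 24% vs 46% | 46% vs 80% | 63% vs 93% |

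At n = 20 the same grid gives 5-39% for the count and 29-97% for the mean.

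At n = 140 the count reaches 26-52% for 5 ms, 69-88% for 8 ms and 91-98% for 10 ms. The mean reaches at least 90% throughout.

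**3. Can a reader interpret a small count?** With no shift at all, SD 15 and n = 40, the chance of at least one patient above 30 ms is 1 - (1 - 0.0228)^40 = 60%. An isolated count therefore says little either way. A mean change would carry a 90% interval of about ±1.645 × 15/√40 = ±3.9 ms.

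**The case against.** - **The SAP does summarize change from baseline.** Counts above 30 and 60 ms are change-from-baseline summaries. Protocol 11.3 does not fix the form, and its preceding sentence limits descriptive statistics to selected criteria. A reader might infer that the SAP drops the change summary altogether; for QTc that is not so. What stands is that the continuous form is missing for every interval, and that heart rate, PR and QRS have no change summary of either kind. The sentence on changes carries no such limit, and Section 11 sets means and medians as the default.
- **The table might still appear.** SAP 3.8 gives a general format for continuous variables, and the table shells are in a separate document not available here. So the table's absence from the final report is an inference, though the natural one, since SAP 6.4 and 6.6 name theirs.
- **The endpoint is a threshold endpoint.** A reader might infer that mean ECG change is itself a secondary endpoint. Protocol 2.4 confines it to clinically significant changes of Grade 3 or above, which cut-points suit. The case rests on Protocol 11.3, not on the endpoint.
- **The comparison flatters the mean.** This stands in part. The exact count test runs below its nominal level, as the worked case shows, but the mean remains well ahead at equal level there.
- **A mean change cannot be pinned on the drug.** This stands. There is no control arm, and Schedule A patients receive dexamethasone, diphenhydramine and acetaminophen before each infusion (Protocol 5.8.1.1). The new table would be descriptive.

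**Conclusion.** The concern holds as a gap between Protocol 11.3 and SAP 6.7, and as a less informative choice of summary. Over the assumed range (SD 12-20 ms, shift 5-10 ms), the mean change is more sensitive than the count above 30 ms in every case examined, so a moderate shift could be missed in a single cohort.

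A reader might go further and infer that a moderate QTc shift at Cmax would usually go unseen. That is not supported. At n = 40 a 10 ms shift is picked up by the count in 50-63% of cases, and a 20 ms shift in about 99% or more. In the pooled 140 patients, 8-10 ms shifts are picked up in 69-98%. The individual values also remain in the listings. All these figures depend on an SD and a shift that the documents do not give. The omission itself does not, and it is worth correcting because the data are already collected.

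**What to change.** Add one descriptive table to SAP 6.7:
- Actual values and change from the Cycle 1 Day 1 pre-dose triplicate mean, for QTcF, heart rate, PR and QRS.
- Each scheduled time point on its own row: end of infusion and 24 hours, shown separately, in Cycles 1 and 3, and end of treatment. Note that the last is a single reading, so it is less precise.
- By dose group or cohort, with n, mean, SD, median, minimum and maximum.

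Keep the categorical QTc table, and state that its Day 1 rows separate pre-dose from end of infusion. A 90% confidence interval for the mean change and a pooled column for expansion patients at 6 mg/kg AIBW would be useful but are optional, since the protocol promises neither.

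The cost is one extra table and a few lines of SAP text. No new visits, samples or patients are needed, and SAP 1.1 allows changes until database lock.
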